12.2. General Statistical Methods

12.2.1. Analysis Sets

The primary endpoint will be assessed in all Treatment subjects who complete the month 3 gap site assessment.

Additional analyses will include all subjects enrolled into the study overall and categorized according to the definitions in section 10.3 or subsets of these categories.

12.2.2. Control of Systematic Error/Bias

Selection of patients will be made from the Investigator's usual patient population. All patients meeting the eligibility criteria and having signed the ICF will be enrolled in the study.

12.2.3. Number of Subjects per Investigative Site

To reduce the impact of individual center, each site may perform up to 30 index ablation procedures. This limit of 30 procedures cannot be exceeded, unless Boston Scientific gives written approval to do so.

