8.1. Scale and Duration

Enrollment will be considered as complete when 60 patients undergo the index ablation procedure and complete encircling of the 4 PVs (2 PV pairs). Up to 6 sites in EU may participate in the study. To reduce the impact of individual center bias, each site may perform up to 30 index ablation procedures. This limit of 30 procedures cannot be exceeded, unless Boston Scientific gives written approval to do so.

[figure not shown]
Each treated subject will be followed for 4 months after the index ablation procedure (index procedure); therefore treated subjects will be followed at index procedure, at pre-discharge visit, at the month 3 assessment and at month 4 follow up.

The study will be considered complete upon completion of the final month 4 follow-up.

A study subject's participation will be considered complete when all protocol required visits have been completed.

It is anticipated that enrollment will be conducted over a period of 6 months; therefore the total study duration is estimated to be 10 months.

Figure 8.1-1: LOCALIZE Study Design

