11.4. Baseline Visit

Subjects who provide consent and meet all of the study enrollment criteria will have baseline data collected.

The data collection at baseline includes:

- Visit date;
- Demographic data, including: age at time of consent, gender;
- Physical assessment including: height, weight, resting heart rate, systolic and diastolic blood pressure; medical history, including:
 - Underlying cardiovascular disease, including but not limited to hypertension, dyslipidaemia, cardiovascular artery disease;
 - Prior history of cardiac events including: acute myocardial infarction, ischemic stroke, hemorrhagic stroke or transient ischemic attack;
 - Prior surgical interventions and/or cardiac procedures (ablation excluded) including: Percutaneous Trans Catheter Angioplasty (PTCA), Coronary Artery Bypass Graft (CABG), pacemaker (PM) implantation, implantable cardioverter-defibrillator (ICD) implant, Cardiac Resynchronization Therapy (CRT) implant, cardiac valve interventions, left atrial appendage closure (LAAC), patent foramen ovale (PFO) intervention, heart transplant or procedures for implantation of other intracardiac devices;

- History of cardiac arrhythmias, including but not limited to time of first episode of PAF;
- Detailed history of all previous cardiac ablation procedures (catheter delivered or surgically performed), if any, including date of latest ablation procedure and any concomitant procedures (e.g., valve surgery, left atrial appendage closure or ligation, etc.), treated arrhythmia(s) and outcome;
- o Pre-procedure assessment of Left Ventricular Ejection Fraction, and left atrial diameter, if available;
- Non-cardiac comorbidities
- CHA2DS2-VASc score
- Current cardiovascular medication regimen including anti arrhythmic, anticoagulation andantiplatelet agents.

11.5. Index (ablation) procedure- Ablating physician BLINDED to DirectSense technology during initial encircling of PVIs (single blind masking)

The index ablation procedure (day 0) should be performed using standard of care methods established by the investigational center (e.g. sterile technique, personnel requirements, etc.). Study-related mapping and ablation with the Rhythmia HDx mapping system, the IntellaMap Orion mapping catheter and the IntellaNav MiFi OI ablation catheter should only be performed by physicians trained in Electrophysiology (EP) and authorized by BSC to perform study-related activities.

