11.5.1. General information

The following general information on the procedure should be collected:

- Procedure date;
- Identification of study devices:
 - o Commercial Rhythmia HDx System; serial number
 - Commercially available Software Version 2.0 with DirectSense technology or any commercially available updates that are released during the course of the study;
 - o The IntellaMap Orion mapping catheter; catheter model, lot number
 - o The IntellaNav MiFi OI ablation catheter; catheter model, lot number
- Identification of non-study devices:
 - o Additional diagnostic catheters used during the case other than Orion including manufacturer, model and type
 - Sheaths used during the procedure including manufacturer, model and type

- Additional ablation catheter(s) used during the case other than IntellaNav MiFi OI including manufacturer, model, and type
- If concomitant procedures occurred during ablation procedure (e.g. ICD implant, PM, LAAC);
- LA access approach (trans septal, retrograde)
- Was heparin administered prior to or immediately following LA access according to guidelines?¹⁷
- Were ACT levels of 300 to 400 seconds achieved during the procedure according to guidelines?¹⁷
- The name of the EP physician performing the procedure

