11.5.2. Procedural information

In order to avoid potential bias, the number of ablating physicians performing the index procedure and the month 3 assessment per investigational site is restricted to 2. Boston Scientific will therefore authorize maximum 2 ablating physicians per site.

Prior to starting the ablations, Rhythmia HDx + IntellaMap Orion will be used to collect an electroanatomic map (i.e. activation and voltage map) of the Left Atrium.

For all subjects it is preferred that all maps are acquired during pacing from the Coronary Sinus.

11.5.2.1. PVI ablation(s) - Ablating physician blinded to the DirectSense technology during initial encircling of PVs

It is recommended to limit the space between the center of 2 lesions to a maximum of 5 mm. The ablating physician is encouraged to avoid jumps between anatomical locations.

For the PVI ablation(s) the following information will be collected:

- Information related to PVI ablation(s):
 - o method of access to left atrium for ablation catheter, if applicable (transseptal, retrograde, or both);
 - type of PVI ablation application(s) (e.g. point (focal) lesions, dragging lesions*);
 - *The usage of dragging lesions for encircling the PVs will result in a Protocol Deviation. Dragging lesions or other types of applications are allowed for other arrhythmia(s)/additional lines.
 - specific PVI ablation technique(s) (WACA + information on additional lines if applicable)
 - o anatomical segments targeted for ablation (please refer to **Figure 11.5-2** for the 8 circumferential positions around each PV pair)
 - **Not targeting all anatomical segments for ablation will result in a Protocol Deviation.

PM007 Confidential

Form/Template 90702637 Rev/Ver AH LOCALIZE protocol, document 92142978, Rev/Ver AB Page 32 of 65

- Total number of RF applications per anatomical segment for PVI ablation;
- Power and duration for each RF application (cfr. printed EP Lab Procedure Report);
- Occurrence of steam pops;
- DirectSense data collection:
 - Blood pool impedance measurements for approximately 10 s prior to the 1st RF application (reference measurement)
 - Myocardium impedance measurements for approximately 10 s prior to the 1st RF application (reference measurement)
 - o Local impedance data will be sampled approximately every 50 ms. This data will be simultaneously recorded in a digital log file by the BSC representative.

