12.1.1.3. Statistical Methods

While no formal hypothesis test will be performed, 95% confidence intervals for the mean difference in baseline Local Impedance/Local Impedance drop values between segments with and without gaps will used to compare groups.

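### The primary impedance comparison pools segments across sites with no site or operator term, although two sites may supply essentially all the data

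*Combined protocol and SAP*

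**What the plan says.** **Size and spread of sites.** Section 8.1 sets the target: "Enrollment will be considered as complete when 60 patients undergo the index ablation procedure", with all four veins encircled. On sites it says "Up to 6 sites in EU may participate in the study", and gives no minimum. Section 12.2.3 adds the cap, "To reduce the impact of individual center, each site may perform up to 30 index ablation procedures", and then the waiver: "This limit of 30 procedures cannot be exceeded, unless Boston Scientific gives written approval to do so".

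**Primary analysis.** Section 12.1.1.3 states that "95% confidence intervals for the mean difference in baseline Local Impedance/Local Impedance drop values between segments with and without gaps will used to compare groups". Neither it nor the synopsis names a site, operator or patient term. Section 12.2.2, on systematic error, deals only with how patients are selected.

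**Conduct.** Section 11.5.2 says that "the number of ablating physicians performing the index procedure and the month 3 assessment per investigational site is restricted to 2", and gives avoidance of bias as the reason. Operators do not see DirectSense values during the first encirclement (8.2.1, 11.5.2.1). Point lesions are expected, since dragging while encircling counts as a deviation, as does leaving a segment untargeted. Lesion spacing of at most 5 mm is a recommendation. Power and duration of each RF application are recorded, but no values are set. Among the index procedure data, section 11.5.1 lists "The name of the EP physician performing the procedure".

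**The concern.** The study asks whether a low baseline LI or a small LI drop at a segment goes with a gap there three months later. A single contrast over all segments mixes two comparisons: gap against gap-free segments within a site, and sites with many gaps against sites with few. Suppose one site has lower impedance readings and also more gaps because of its power and duration settings, or because it calls gaps more readily. The pooled contrast then shows a difference even if impedance and gaps are unrelated within each site. The opposite pattern hides a real relation.

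The study is meant to inform usage guidance and a future lesion index (section 6), and both need a relation that holds in a given operator's hands. The fewer the sites, the more a single between-site difference can weigh. A cap at half the target leaves room for a two-site study. Allowing for correlation within patients corrects the width of the interval, but does not by itself remove a shift between sites.

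**Working it through.** **1. How far the cap limits concentration.** 60 subjects / 30 procedures = 2 sites, each with 30/60 = 50% of the data. An even spread over six sites would give 60/6 = 10 each. With at most two physicians per site, a two-site study rests on two to four operators. One qualification applies: the cap counts procedures, while the target counts Treatment subjects, and ATTEMPT subjects (section 10.3) do not count towards the target. Two sites therefore reach exactly 60 only with no ATTEMPT case or with a waiver. At an assumed 98% completion rate, the expected yield is 60 x 0.98 = 58.8, and the chance of all 60 is 0.98^60 = 0.30.

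**2. The plan's own yardstick.** Section 12.1.1.2 gives 90% power at 3.71 ohm with 50 usable patients. This cannot be reproduced, because neither the SD nor the gap rate is stated. Treating 50 x 16 = 800 segments as independent (two-sided 5%), the implied SD is 7.1 ohm at a 5% gap rate, 9.7 at 10% and 13.0 at 20%. Below, 3.71 ohm serves only as a scale.

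**3. Shift from site differences alone.** Assume two sites with equal numbers of segments, gap rates p1 and p2, mean impedances D ohm apart, and no association within either site.
- Site 1's share of gap segments: p1/(p1 + p2).
- Site 1's share of gap-free segments: (1 - p1)/(2 - p1 - p2).
- Shift in the pooled difference: D x (difference of the two shares).

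| Gap rates | Shares | Multiplier | D = 5 | D = 10 | D = 15 |
|---|---|---|---|---|---|
| 15% and 5% | 0.750, 0.472 | 0.278 | 1.4 ohm | 2.8 ohm | 4.2 ohm |
| 12% and 8% | 0.600, 0.489 | 0.111 | 0.6 ohm | 1.1 ohm | 1.7 ohm |

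One of the six entries exceeds 3.71 ohm. To produce all of 3.71 ohm at 15% and 5%, site means would have to be about 3.71/0.278 = 13 ohm apart.

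**4. Effect on the interval.** This was simulated with 4,000 runs per setting: 50 patients x 16 independent segments, two sites of 25 patients, gap rates 5% and 15%, no within-site association. The table shows how often the 95% interval excludes zero.

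| SD | D | Pooled | Site-adjusted |
|---|---|---|---|
| 10 | 3 | 11% | 5% |
| 10 | 5 | 21% | 5% |
| 10 | 8 | 45% | 5% |
| 7 | 5 | 36% | 5% |

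With gap rates of 5% and 10%, SD 10 and D = 5, the pooled figure is 11%. With six sites spread evenly over the 5% to 15% gap range and a 5 ohm range of means, at SD 10, it is 9.5% with an average shift of 0.7 ohm. More sites make the problem smaller but do not remove it.

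All gap rates, SDs and site differences in steps 3 and 4 are assumptions; the documents give none.

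**The case against.** The strongest case against runs as follows. The study is descriptive and tests no hypothesis. Section 12 presents itself as an overview, so pooling is read from silence. The plan already has design controls, and the data needed for adjustment are collected, so it could be added later and reported under 12.3.2. Most of this is true, but the interval in 12.1.1.3 is still the primary result. As written it is a pooled contrast, and an adjustment chosen after seeing the data carries less weight than one fixed beforehand.

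Four stronger readings are tempting, and the documents do not support them.
- *That the cap is the only control of centre effects.* The physician limit, blinding, the point-lesion rule and the requirement to target every segment also act on it. They narrow differences between sites without adjusting for those that remain.
- *That each centre ablates in its own way.* Section 11.5 does say the procedure "should be performed using standard of care methods established by the investigational center", but its examples concern general conduct, such as sterility and staffing. Section 11.5.2 partly standardises the lesions. The firmer ground is that power and duration are left open.
- *That operator technique alone can produce the result.* Bias needs sites to differ in both impedance and gap rate, by a route other than impedance. An operator with better coupling, larger drops and fewer gaps shows the association under study.
- *That whoever ablated also calls the gaps.* Section 11.5.2 limits each site to two physicians but does not require the same one at both procedures for a given patient.

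**Conclusion.** The concern holds in a limited form. The primary contrast has no site or operator term, and the design allows two sites to supply essentially all 60 subjects. If sites differ in both mean impedance and gap rate for reasons other than impedance, the pooled estimate is biased. Under the assumed two-site case with gap rates of 15% and 5%, the shift is 0.28 ohm per ohm of between-site difference. For differences of 5 to 10 ohm that is 1.4 to 2.8 ohm, short of 3.71 ohm but enough to move the interval off zero more often than it should. It falls to 0.11 per ohm at gap rates of 12% and 8%, and is smaller with more sites.

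A reader might infer that the study's finding would be an artefact of who ablated. The documents give no gap rates or site differences, so they show that this bias is possible and unadjusted for, not that it will be large. The point merits a change before analysis because adjustment is cheap and the index operator is already recorded.

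**What to change.** **In 12.1.1.3**, pre-specify the mean difference in baseline LI and in LI drop, each with its 95% confidence interval, estimated with site as a stratum or fixed effect and with allowance for clustering of segments within patients. Use index operator in place of site where numbers allow, and say that the index operator is meant: the physician's name is listed for the index procedure (11.5.1) but not among the month 3 items in 11.9. Report this estimate beside the pooled one.

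**In 8.1 and 12.2.3**, keep the cap as a limit on any one site's share, but do not rely on it to handle centre effects; point to the adjusted estimate instead. Removing the waiver would not be enough, since two sites at 30 each would still be allowed.

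**Do not require separate estimates per operator.** With 6 x 2 = 12 operators, 800 segments give about 67 each. At an assumed gap rate of 5% to 10%, that is only 3 to 7 gap segments per operator.

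**Cost.** A short addition to the analysis section and small edits to two others, with no new data. A few degrees of freedom are lost, and sites or operators without gaps contribute nothing to the adjusted contrast. The adjustment also removes any genuine between-operator signal, which is why the pooled estimate stays alongside.

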12.3. Data Analyses

12.3.1. Other Endpoints/Measurements

Additional analyses are planned, including but not limited to:

- Correlation of DirectSense parameters and acute PVI gaps
 - Acute isolation gaps per anatomical segment as associated with baseline Local Impedance and Local Impedance drop values at first pass encircling during the index ablation procedure
- Median number of gaps per patient (or per PV pair) after initial encircling;
- Statistical characterization of impedance readings for each ablation point
- Anatomical distribution of the gaps and impedance reading differences at different anatomical sites (PV segments)

12.3.2. Changes to Planned Analyses

Any changes to the planned statistical analyses outlined in this protocol will be documented in the clinical study report along with a reason for the deviation.

13. Data Management

13.1. Data Collection, Processing, and Review

Subject data will be recorded in a secure electronic data capture (EDC) system.

The clinical database will reside on a production server hosted by EDC System. All changes made to the clinical data will be captured in an electronic audit trail and available for review by the Sponsor or its representative. The associated iMedidata RAVE software and database have been designed to meet regulatory compliance for deployment as part of a validated system compliant with laws and regulations applicable to the conduct of clinical studies

Form/Template 90702637 Rev/Ver AH LOCALIZE protocol, document 92142978, Rev/Ver AB Page 43 of 65

pertaining to the use of electronic records and signatures. Database backups are performed regularly.

The Investigator provides his/her electronic signature on the appropriate eCRFs in compliance with local regulations. Changes to data previously submitted to the sponsor require a new electronic signature by the Investigator acknowledging and approving the changes.

Visual and/or electronic data review will be performed to identify possible data discrepancies. Manual and/or automatic queries will be created in the EDC system and will be issued to the site for appropriate response. Site staff will be responsible for resolving all queries in the database.

13.2. Rhythmia HDx Electronic Data Management

At the conclusion of the case, de-identified case data will be exported in a proprietary format from both the Rhythmia HDx mapping system to external storage media (as provided by the sponsor) and provided back to the sponsor.

13.3. Data Retention

The Investigator or Investigational site will maintain, at the investigative site, in original format all essential study documents and source documentation that support the data collected on the study subjects in compliance with ICH/GCP guidelines. Documents must be retained until at least 2 years have elapsed since the formal discontinuation of the clinical investigation of the product. These documents will be retained for a longer period of time by agreement with BSC or in compliance with other local regulations. It is BSC's responsibility to inform the Investigator when these documents no longer need to be maintained. The Investigator will take measures to ensure that these essential documents are not accidentally damaged or destroyed. If for any reason the Investigator withdraws responsibility for maintaining these essential documents, custody must be transferred to an individual who will assume responsibility, and BSC must receive written notification of this custodial change.

13.4. Technical Source Forms

A Technical Source Form (TSF) is developed by Boston Scientific or by the investigational site to capture protocol required data elements that are not duplicated in any other source documents. This form is to be used by the study sites as a source document. A Boston Scientific representative (R&D Representative or Clinical Trial Manager) may complete the TSF at the request of the Ablating Physician. The TSF will be reviewed and signed for approval by the Ablating Physician at the end of each procedure.

14. Amendments

If a protocol revision is necessary which affects the rights, safety or welfare of the subject or scientific integrity of the data, an amendment is required. Appropriate approvals (e.g., EC/CA) of the revised protocol must be obtained prior to implementation.

15. Deviations

An Investigator must not make any changes or deviate from this protocol, except to protect the life and physical well-being of a subject in an emergency. An investigator shall notify the sponsor and the reviewing EC of any deviation from the investigational plan to protect the life or physical well-being of a subject in an emergency, and those deviations which affect the scientific integrity of the clinical investigation. Such notice shall be given as soon as possible, but no later than 5 working days after the emergency occurred, or per prevailing local requirements, if sooner than 5 working days.

All deviations from the investigational plan, with the reason for the deviation and the date of occurrence, must be documented and reported to the sponsor in the eCRF. Sites may also be required to report deviations to the EC, per local guidelines and government regulations.

Deviations will be reviewed and evaluated on an ongoing basis and, as necessary, appropriate corrective and preventive actions (including EC notification, site re-training, or site discontinuation/termination) will be put into place by the sponsor.

16. Device/Equipment Accountability

The principal investigator or an authorized designee shall keep records documenting the

- Rhythmia HDx system unit number, software version used, date used
- Model number, serial number, and date used of the catheters

17. Compliance

17.1. Statement of Compliance

This study will be conducted in accordance with the current version of ISO 14155: Clinical Investigation of Medical Devices for Human Subjects – Good Clinical Practice, the relevant parts of the ICH Guidelines for Good Clinical Practice, relevant parts of the ICH Guidelines for Good Clinical Practices, ethical principles that have their origins in the Declaration of Helsinki, and pertinent individual country laws and regulations. The study shall not begin until the required approval/favorable opinion from the EC and/or regulatory authority has been obtained, if appropriate. Any additional requirements imposed by the EC or regulatory authority shall be followed, if appropriate.

